# **Document History**

Document	Version Date
Original protocol	18 December 2023

#### 1. PROTOCOL SUMMARY

## 1.1. Synopsis

**Protocol Title:** A Phase 1/2 Randomized Study to Evaluate the Safety, Tolerability, and Immunogenicity of a Modified RNA COVID-19 Vaccine and a Recombinant Influenza Vaccine Administered as a Single Injection in Healthy Adults 50 Years of Age or Older

**Brief Title:** A Study to Evaluate the Safety, Tolerability, and Immunogenicity of a COVID-19 Vaccine and an Influenza Vaccine Given as a Single Injection in Healthy Adults

## **Regulatory Agency Identification Number(s):**

US IND Number:

EudraCT/EU CT Number:

Not Applicable
ClinicalTrials.gov ID:

Not Available
Pediatric Investigational Plan Number:

Not Applicable
Protocol Number:

C5681001
Phase:

#### **Rationale:**

BNT162b2 (Comirnaty®) is a messenger ribonucleic acid (mRNA)-based vaccine that, as of January 2023, has been granted full marketing authorization, conditional marketing authorization, emergency use authorization (EUA), or temporary authorization in a total of more than 184 countries for the prevention of coronavirus disease 2019 (COVID-19) caused by severe acute respiratory syndrome coronavirus 2 (SARS-CoV-2). The original version of BNT162b2 encodes the ancestral Wuhan-Hu-1 strain spike glycoprotein. In the United States (US), it has been fully licensed for use in individuals 12 years of age and above as of 08 July 2022. All versions of the vaccine encode the SARS-CoV-2 spike protein(s) in nucleoside-modified messenger ribonucleic acid (modRNA) encapsulated in ribonucleic acid lipid nanoparticles (RNA-LNPs), which has demonstrated potent immunogenicity, high vaccine efficacy (VE), and a favorable safety profile in Phase 1, 2, and 3 human trials, as well as in real-world usage. As SARS-CoV-2 continues to circulate, at very high levels, Pfizer/BioNTech are investigating RNA-based COVID-19 vaccines to further protect against COVID-19 caused by emergent and potentially more antigenically diverse variants. BNT162b2 (Omicron [Omi] XBB.1.5), a monovalent vaccine containing mRNA encoding the spike protein of the XBB.1.5 variant, will be used in this study as this is the variant recommended by the Food and Drug Administration (FDA) beginning in fall 2023.

Flublok Quadrivalent (referred to as RIV [recombinant influenza virus]) is a recombinant influenza vaccine, manufactured in a baculovirus expression vector and insect cell culture system, consisting of 4 recombinant influenza hemagglutinin (HA) antigens derived from influenza virus type A, subtypes H1 and H3, and 2 type B virus strains (lineages B/Victoria and B/Yamagata). HA genes from each of the 4 influenza viruses are inserted into a plasmid baculovirus expression vector system (BEVS) and expressed in *Spodoptera frugiperda* insect cells. RIV is indicated for active immunization against influenza disease caused by influenza A subtype viruses and type B viruses contained in the vaccine, for use in adults 18 years and older.

Annual vaccine programs for SARS-CoV-2 are likely to run concurrently with annual influenza campaigns. In practice, BNT162b2 may be given simultaneously with licensed influenza vaccines.

Combining BNT162b2 with RIV in a single injection would increase the likelihood that persons seeking either vaccination against SARS-CoV-2 or influenza would opt to protect themselves against both pathogens.

This Phase 1/2 study will evaluate the safety, reactogenicity, and immunogenicity of BNT162b2 (Omi XBB.1.5) and RIV administered as a mixture in a single injection.

## Objectives, Endpoints, and Estimands:

Objectives	Endpoints	Estimands	
Primary:	Primary:	Primary:	
Safety	l		
To describe the safety and tolerability of the study interventions	
 
Local reactions (pain at the injection site, redness, and swelling)
 
Systemic events (fever, fatigue, headache, chills, vomiting, diarrhea, new or worsened muscle pain, and new or worsened joint pain)
 
Adverse events (AEs)
 
Serious adverse events (SAEs)
 
	The percentage of participants receiving at least 1 dose of study intervention reporting:  • Local reactions for up to 7 days following vaccination  • Systemic events for up to 7 days following vaccination  • AEs from vaccination through 4 weeks after vaccination  • SAEs from vaccination through 6 months after vaccination	

Objectives	Endpoints	Estimands
Immunogenicity		
To describe the immune responses elicited by BNT162b2 (Omi XBB.1.5)/RIV, BNT162b2 (Omi XBB.1.5) + RIV coadministered, and BNT162b2 (Omi XBB.1.5) and RIV administered alone (4 weeks after vaccination)	SARS-CoV-2 Omicron (XBB.1.5)—neutralizing titers	In participants complying with the key protocol criteria (evaluable participants):  • Geometric mean titers (GMTs) before vaccination and at 4 weeks after vaccination  • Geometric mean fold rise (GMFR) from before vaccination to 4 weeks after vaccination  • Percentage of participants with seroresponse a at 4 weeks after vaccination
	Hemagglutinin inhibition assay (HAI) titers against the seasonal strains recommended by the World Health Organization (WHO) for the northern hemisphere 2023-2024 influenza season	
 
In participants complying with the key protocol criteria         (evaluable participants):         
 
GMTs before vaccination and at 4 weeks after vaccination
 
 
 
GMFRs from before vaccination to 4 weeks after vaccination
 
The percentages of participants achieving HAI seroconversionb at 4 weeks after vaccination
 
The percentages of participants with HAI titers ≥1:40 before vaccination and at 4 weeks after vaccination
 

- a. Seroresponse is defined as achieving a ≥4-fold rise from baseline (before the study vaccination). If the baseline measurement is below the lower limit of quantitation (LLOQ), the postvaccination measure of ≥4 × LLOQ is considered seroresponse.
- b. Seroconversion is defined as an HAI titer <1:10 prior to vaccination and ≥1:40 at the time point of interest, or an HAI titer of ≥1:10 prior to vaccination with a minimum 4-fold rise at the time point of interest.

## **Overall Design:**

This is a Phase 1/2 single-blind (site- and sponsor-unblinded) study to evaluate the safety, tolerability, and immunogenicity of licensed BNT162b2 (Omi XBB.1.5) and RIV administered together as a single injection (referred to as BNT162b2 [Omi XBB.1.5]/RIV) in healthy adults 50 years of age or older.

The safety, tolerability, and immunogenicity of BNT162b2 (OmiXBB1.5)/RIV administered as a single injection will be compared to BNT162b2 (Omi XBB.1.5) + RIV administered simultaneously as 2 separate injections (coadministered), and to BNT162b2 (Omi XBB.1.5) or RIV when administered alone.

Across Phases 1 and 2, approximately 640 participants in total will be randomized with an equal randomization ratio (1:1:1:1) to each of the following vaccine groups and stratified by age group (50 through 64 years of age and ≥65 years of age):

- **Group 1:** BNT162b2 (Omi XBB.1.5)/ RIV (as a single injection) administered in the left deltoid and placebo administered in the right deltoid
- Group 2: BNT162b2 (Omi XBB.1.5) administered in the left deltoid and RIV administered in the right deltoid
- **Group 3:** BNT162b2 (Omi XBB.1.5) administered in the left deltoid and placebo administered in the right deltoid
- **Group 4:** RIV administered in the left deltoid and placebo administered in the right deltoid

During Phase 1, a total of  $\sim$ 20 participants will be enrolled in each vaccine group. Enrollment of participants in each vaccine group will be controlled such that  $\sim$ 10 participants 50 through 64 years of age (sentinel participants, considered Phase 1a) can be vaccinated in each of the groups on the first day. This will be monitored by the sponsor, who will inform sites to pause enrollment once the target has been reached. Vaccination of the remaining  $\sim$ 40 participants ( $\sim$ 10 per vaccine group) will commence no sooner than 24 hours after this safety pause. The participants vaccinated after the safety pause will be  $\geq$ 65 years of age (considered Phase 1b).

Once ~20 participants per vaccine group have been vaccinated in Phase 1, the interactive response technology (IRT) system will block any further randomization, pending a review of at least 72 hours of safety data for all participants by the internal review committee (IRC). The outcome of the safety data review will be documented in a memo, which will be circulated to all sites prior to starting enrollment in Phase 2. In Phase 2, approximately 140 participants 50 years of age or older will be enrolled in each of the 4 vaccine groups. Participants will be stratified by age group, 50 through 64 years of age and ≥65 years of age.

Prespecified local reaction and systemic event data will be collected in an electronic diary (e-diary) during the 7 days, or longer for ongoing symptoms, after study intervention (ie, from Day 1, the day of vaccination, until symptom resolution), as well as any medications taken during this period to treat any pain symptoms or fever.

Blood samples of approximately 20 mL will be collected from all participants for immunogenicity assessments prior to vaccination and at 4 weeks and 6 months after vaccination.

Following vaccination, AEs will be collected from informed consent signing through Visit 2 (approximately 4 weeks after vaccination), and SAEs will be collected from informed consent signing through Visit 3 (approximately 6 months after vaccination). In addition, AEs occurring up to 48 hours after blood draws will also be collected.

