#### 1.2. Schema

Phase 1 N = 80							
Group 1 BNT162b2/RIV (1.0 mL) + placebo (0.5 mL)	Group 2 RIV (0.5 mL) + BNT162b2 (0.3 mL)	Group 3 BNT162b2 (0.3 mL) + placebo (0.5 mL)	Group 4 RIV (0.5 mL) + placebo (0.5 mL)				
. , ,	Phase 1a (Participants 50 through 64 years of age)						
Sentinel	Sentinel	Sentinel	Sentinel				
n = 10	n = 10	n = 10	n = 10				
Sponsor Safety Data Review a Phase 1b (Participants ≥65 years of age)							
n = 10	n = 10 $n = 10$ $n = 10$						
$IRC^b$							
Phase 2 N = 560							
Participants ≥50 years of age							
n = 140							

- a. Progression of the study will occur upon confirmation of an acceptable safety assessment of data accumulated after at least 24 hours and up to 7 days after vaccination.
- b. Progression of the study will occur upon confirmation of an acceptable safety assessment of data accumulated after at least 72 hours and up to 7 days after vaccination, once approximately 20 participants in each vaccine group have been vaccinated.

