**Table 1. Schedule of Activities** 

Visit Identifier	1	2	3	Notes
Visit Window	Day 1	28 to 35 Days After Visit 1	175 to 189 Days After Visit 1	Day 1 = Day of Vaccination
Visit Description	Vaccination	4-Week Follow-Up Visit	6-Month Follow-Up Visit	
Visit Type/Location	Site	Site	Site	
Confirm use of contraceptives (if appropriate)	X	X		See Section 5.3.1 for additional information.
Confirm eligibility	X			See Section 5 for additional information.
Review temporary delay criteria	X			See Section 5.5 for additional information.
Obtain randomization number and study intervention allocation	X			At registration, the participant enrollment number and dose-level allocation are assigned.
Collect blood sample for immunogenicity assessment	~20 mL	~20 mL	~20 mL	
 
See Section 8.2 for additional information.
 
For laboratory collection volumes, see the laboratory manual.
 

Administer study intervention	X			
Postvaccination observation (at least 30 minutes) and assessment of immediate events	X			
Explain participant communication methods (including for reactogenicity e-diary completion), assist the participant with downloading the application, or issue provisioned device, if required	X			See Section 8.3.4 for additional information.
Provide/ensure the participant has a thermometer and measuring device	X			
Review reactogenicity e-diary data (daily review is optimal during the active reactogenicity e-diary period [Days 1 through 7])	•	•		

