# **Table 1. Schedule of Activities**

Visit Identifier	1	2	3	Notes
Visit Window	Day 1	28 to 35 Days After Visit 1	175 to 189 Days After Visit 1	Day 1 = Day of Vaccination
Visit Description	Vaccination	4-Week Follow-Up Visit	6-Month Follow-Up Visit	
Visit Type/Location	Site	Site	Site	
Site reviews e-diary data with participant follow-up until ongoing symptom/medication resolution, if applicable		X	X	Review the participant's e-diary data and record assessment in the CRF. Assess compliance, and any medically attended events (including hospitalizations). For symptoms still ongoing, continue to follow up until resolution, and document and record stop dates in the CRF.
Collect reactogenicity e-diary medication use		X		
Collect AEs and SAEs as appropriate	X	X	X	
 
See Section 8.4 for additional information.
 
AEs are collected from the completion of informed consent through Visit 2. SAEs are collected from the completion of informed consent through the end of study participation. Additionally, any AEs occurring up to 48 hours after a blood draw must be recorded.
 

Collect e-diary or assist the participant with deleting the application		X		

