# 8.3.4. Electronic Diary

All participants will be required to complete a reactogenicity e-diary after vaccination given at Visit 1, through an application installed on a provisioned device or on the participant's own personal device. All participants will be asked to monitor and record local reactions, systemic events, and use of any medication for solicited pain symptoms or fever for 7 days, or longer for ongoing symptoms, from the day of administration of the study intervention given at Visit 1. The reactogenicity e-diary allows recording of these assessments each day, thus providing the accurate representation of the participant's experience. Data on local reactions and systemic events reported in the reactogenicity e-diary will be transferred electronically to a third-party vendor, where they will be available for review by investigators and the Pfizer clinicians at all times via an internet-based portal.

At intervals agreed to by the vendor and Pfizer, these data will be transferred electronically into Pfizer's database for analysis and reporting. Generally, these data do not need to be reported by the investigator in the CRF as AEs. However, if a participant has a serious adverse event reported in the e-diary, the event(s) should be recorded on the CRF, regardless of whether the investigator considers the event(s) to be related. If a participant missed reporting an event in the e-diary and reports it to the study site instead, the event should also be recorded on the CRF.

Investigators (or designee) will be required to review the reactogenicity e-diary data online at frequent intervals to evaluate participant compliance and as part of the ongoing safety review.

The investigator or designee must obtain stop dates from the participant for any symptoms ongoing on the last day from Day 7 onwards and follow up daily until resolution. The stop dates should be documented in the source documents and the information entered in the CRF.

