# **Stopping Rule Criteria for Each Vaccine Group:**

- If any vaccinated participant develops an SAE that is assessed by the investigator as possibly related to the study intervention, or for which there is no alternative, plausible, attributable cause.
- If any participant develops a Grade 4 local reaction or systemic event after vaccination (see Section 8.3.4) that is assessed as possibly related by the investigator, or for which there is no alternative, plausible, attributable cause.

- If any participant develops a fever >40°C (>104.0°F) for at least 1 daily measurement after vaccination (see Section 8.3.4.4) that is assessed as possibly related by the investigator, or for which there is no alternative, plausible, attributable cause.
- If any vaccinated participant develops confirmed myocarditis or pericarditis.
- If any vaccinated participant dies.
- If any vaccinated participant experiences a Grade 4 unsolicited AE, or SAE of any severity, assessed as related to the study intervention by the investigator.
- If any 2 participants vaccinated participants develop the same or similar Grade 3 or higher unsolicited AE, other than myocarditis/pericarditis, assessed as related to study intervention by the investigator. Note that the solicited local reactions, systemic events, and fever specified in Section 8.3.4, reported within 7 days from the day of administration of the study intervention, irrespective of whether they are recorded in the e-diary or as AEs, are excluded from this stopping rule.

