# 8.4.1. Time Period and Frequency for Collecting AE and SAE Information

The time period for actively eliciting and collecting AEs and SAEs ("active collection period") for each participant begins from the time the participant provides informed consent, which is obtained before the participant's participation in the study (ie, before undergoing any study-related procedure and/or receiving study intervention), through and including Visit 2. At Visit 3 (approximately 6 months after vaccination), the participant will be asked about AESIs since Visit 1.

Additionally, any AEs occurring up to 48 hours after any subsequent blood draws must be recorded in the CRF.

SAEs will be collected from the time the participant provides informed consent through the duration of the study (Visit 3, approximately 6 months after vaccination).

Follow-up by the investigator continues throughout the active collection period and until the AE or SAE or its sequelae resolve or stabilize at a level acceptable to the investigator.

When a clinically important AE remains ongoing at the end of the active collection period, follow-up by the investigator continues until the AE or SAE or its sequelae resolve or stabilize at a level acceptable to the investigator and Pfizer concurs with that assessment.

For participants who are screen failures, the active collection period ends when screen failure status is determined.

If the participant withdraws from the study and also withdraws consent for the collection of future information, the active collection period ends when consent is withdrawn.

If a participant permanently discontinues or temporarily discontinues from the study because of an AE or SAE, the AE or SAE must be recorded on the CRF and the SAE reported using the Vaccine SAE Report Form or via PSSA.

Investigators are not obligated to actively seek information on AEs or SAEs after the participant has concluded study participation. However, if the investigator learns of any SAE, including a death, at any time after a participant has concluded study participation, and they consider the event to be reasonably related to the study intervention, the investigator must promptly report the SAE to Pfizer using the Vaccine SAE Report Form or via PSSA.

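### No adverse-event inquiry is scheduled before the two Phase 1 safety reviews, and the stopping rules can end before a late Visit 2

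*Protocol*

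**What the plan says.** Phase 1 has two safety reviews. The sponsor's review separates Phase 1a (about 10 per group, aged 50 through 64) from Phase 1b (about 10 per group, aged 65 and older). For it, footnote a of the schema in Protocol Section 1.2 asks for an "acceptable safety assessment of data accumulated after at least 24 hours and up to 7 days after vaccination". The IRC review separates Phase 1 from Phase 2. The synopsis (Overall Design) blocks randomization "pending a review of at least 72 hours of safety data for all participants by the internal review committee (IRC", and schema footnote b asks for an "acceptable safety assessment of data accumulated after at least 72 hours and up to 7 days after vaccination". SAP Section 2.3 repeats both conditions.

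In Table 1 (Section 1.3) the row "Collect AEs and SAEs as appropriate" is marked at Visits 1, 2 and 3 only, and Visit 2 falls 28 to 35 days after Visit 1. The one activity placed between Visits 1 and 2 is e-diary review, where "daily review is optimal during the active reactogenicity e-diary period". Section 8.3.4 sets what the diary holds: "All participants will be asked to monitor and record local reactions, systemic events, and use of any medication for solicited pain symptoms or fever".

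Section 8.3.5 bases the Phase 1 stopping rules on AE data as well as diary data. One rule pauses a vaccine group if two participants "develop the same or similar Grade 3 or higher unsolicited AE" judged related; solicited reactions within 7 days do not count toward it. The rules stay in force until Phase 2 starts or until 30 days after the last Phase 1 dose, whichever is later.

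Section 8.4.1 defines "The time period for actively eliciting and collecting AEs and SAEs" as running from consent through Visit 2, and Section 8.4 requires nonleading questioning within it. Neither section gives a date between the visits.

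**The concern.** The two-participant rule needs unsolicited AEs, but the only data stream scheduled before either review carries solicited ones. For part of the AE record, then, a blank entry can mean that nothing happened or that nobody has asked yet, and the reviewing body cannot tell which.

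The synopsis (Ethical Considerations) acknowledges that the risks of giving the two vaccines as one injection are not fully known. These two reviews decide whether the mixture goes to older participants and then to Phase 2.

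The second issue is the end date of the rules. Visit 2 is where AEs are next asked about, and its window runs to day 35. Rules that can lapse on day 30 may be gone before some of those answers arrive. A late report would then fall to the IRC's general monitoring (Section 10.1.5.1) instead of a stated pause criterion.

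**Working it through.** **1. The plan's own figure.** Table 7 (Section 9.5) uses P(at least 1 event) = 1 − (1 − p)^n.
- p = 0.01, n = 160: 1 − 0.99^160 = 0.7997, printed as 0.80.
- p = 0.05, n = 20: 1 − 0.95^20 = 0.6415, printed as 0.64.

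The table is correct. It concerns whether an event occurs in the group, not when the site learns of it.

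**2. Routes by which an event reaches the site before Visit 2.**

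| Event | Route | Section |
|---|---|---|
| Solicited, Grade 3 or suspected Grade 4 | Diary entry, then telephone contact | 8.3.4, 8.10.4 |
| Medically attended, or hospitalization | Participant told to contact site | 8.10.1 |
| Chest pain, shortness of breath, palpitations | Participant told to contact site | 8.10.1 |
| Severe systemic event, Days 1 to 7 | Participant told to contact site at once | 8.10.1 |
| Any other health change | General reminder, undated | 8.1.1 |
| Unsolicited, related, Grade 3, not medically attended, not volunteered | Nothing scheduled | none |

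The last class is narrow but not empty. Section 2.3.1 lists lymphadenopathy, rash, pruritus and urticaria among the key risks identified for BNT162b2, and none is a diary item. Appendix 3 defines Grade 3 by significant interference with usual function, which does not require medical care.

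**3. Time from a participant's data cut to that participant's Visit 2.**
- Sponsor review, data at 1 to 7 days: 28 − 7 = 21 to 35 − 1 = 34 days.
- IRC review, for a participant with 3 to 7 days of data: 28 − 7 = 21 to 35 − 3 = 32 days.

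The second range fits mainly Phase 1b. Phase 1a participants are dosed earlier and may have longer follow-up by the IRC review. If Phase 1b fills slowly, some may already have had Visit 2.

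**4. Rule coverage of Visit 2.** Count days from the last Phase 1 dose. Let s be the day Phase 2 starts, so the rules end on E = max(s, 30). A participant dosed k days before the last dose, with Visit 2 on own day d (28 to 35), is covered if d − k ≤ E. Uncovered days = max(0, 35 − k − E).

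If Phase 2 starts by day 30 (E = 30):

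| k | 0 | 1 | 2 | 3 | 4 | 5 or more |
|---|---|---|---|---|---|---|
| Covered days of 8 | 3 | 4 | 5 | 6 | 7 | 8 |
| Uncovered days of 8 | 5 | 4 | 3 | 2 | 1 | 0 |

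For the last-dosed (k = 0), with a later Phase 2 start:

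| s | 31 | 32 | 33 | 34 | 35 or later |
|---|---|---|---|---|---|
| Uncovered days of 8 | 4 | 3 | 2 | 1 | 0 |

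**5. Illustration with assumed rates.** The documents give neither the risk of a qualifying event nor the share known at a review. Let p be the assumed risk that such an event has begun by the IRC review, c the assumed share known, and r = p × c. With 20 independent participants per group, P(2 or more known) = 1 − (1 − r)^20 − 20r(1 − r)^19.

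| p | c = 1 | c = 0.5 | c = 0.25 | c = 0 |
|---|---|---|---|---|
| 5% | 0.26 | 0.09 | 0.03 | 0 |
| 10% | 0.61 | 0.26 | 0.09 | 0 |
| 20% | 0.93 | 0.61 | 0.26 | 0 |

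This shows how incomplete capture weakens the rule at that review. It does not estimate the rule's performance in this trial.

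**The case against.** The strongest reply is that the process exists and only a dated telephone call is missing. The synopsis asks for safety data on all participants, not diary data alone. Section 8.3.5 has investigator and sponsor monitoring continuously, Section 8.4 requires questioning, and Section 8.1.1 permits telehealth contacts and requires reminders to report health changes. The immediate call-in instruction for severe systemic events covers Days 1 to 7, the window of both reviews. The protocol elsewhere uses that term for the solicited list, but a participant with a severe unlisted symptom might well act on it. The IRC charter, which is not among the documents, may already require AE confirmation. Both components are licensed at these doses, so only the mixing is new.

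Much of this stands. It limits the exposed class to events that pass every one of these routes, and the two-participant rule also needs a similar event in a second member of the same group. It does not close the gap: none of these provisions sets an AE contact before either review, and monitoring acts only on what has been received.

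A reader might infer three stronger things that the documents do not support:
- That the two-participant rule cannot work in Phase 1. It can act on volunteered reports, and on Visit 2 reports while it is in force.
- That every participant is at least 21 days short of Visit 2 at the IRC review. Phase 1a participants need not be.
- That SAEs, Grade 4 events or cardiac symptoms go unseen. Call-in instructions make these much less exposed.

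**Conclusion.** The point holds in limited form. A related, Grade 3, unsolicited AE that is neither medically attended nor volunteered may be unknown at the sponsor review and, mainly for Phase 1b, at the IRC review. No detection probability can be derived from the documents.

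The lapse of the rules is conditional. It needs Phase 2 to start before day 35 after the last Phase 1 dose, a participant dosed within 4 days of that dose, and a late Visit 2. The worst case is 5 of 8 permitted days, for the last-dosed when Phase 2 starts by day 30. The count assumes Visit 2 takes place in its window and that a report on the rules' final day still counts.

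Both changes are worth making because they are cheap, although the exposed class is small. Confidence is medium. If the IRC charter already requires AE confirmation before the data cut, adding the IRC-stage calls only brings the schedule into line with it.

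**What to change.** 1. **Section 8.3.5.** Run the stopping rules until the later of the Phase 2 start and the last Phase 1 participant's Visit 2, using day 35 after the last Phase 1 dose if that visit is missed. Cost: one line of text and up to 35 − 30 = 5 more days of rule monitoring.
2. **Table 1 and Section 8.10.1.** Add one brief, scripted, nonleading AE/SAE telephone inquiry before each data cut: for the 40 Phase 1a participants before the sponsor's review, and for all 80 Phase 1 participants before the IRC review. Record answers of none and include them in the data reviewed. After a set number of failed attempts, list the participant as not reached so that one unanswered call does not hold up the study.

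The second change costs about 40 + 80 = 120 short calls by existing site staff, within the 7-day span that the schema footnotes allow. It needs no new site visits, samples or participants. Its limit is that a call finds only events that have begun. At the 24-hour minimum it adds about one day beyond the Day 1 observation, and later-onset events still wait for Visit 2 or a volunteered report.
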